6. DOSAGE AND ADMINISTRATION

Subjects will be randomly assigned to receive unblinded, flexible dosages of topiramate or levetiracetam as follows:

- Topiramate: weight-based dosing for subjects 2 to <10 years of age, not to exceed 350 mg/day, as tolerated; not to exceed 400 mg/day in subjects 10 to 15 years of age, as tolerated
- Levetiracetam: weight-based dosing for all subjects 2 to 15 years of age, not to exceed 60 mg/kg/day, as tolerated

Subjects will receive study drug in a twice-a-day regimen (BID). The first dose of study drug on Day 1 will be taken in the evening. After randomization, subjects will be titrated as tolerated to the maximum recommended dosage for optimal clinical effect over 6 to 8 weeks and will be maintained on that dosage through the open-label treatment phase, with the option for dosage adjustment as required for optimal clinical effect. Changes to this schedule will be based on a risk-benefit assessment of the subject's clinical condition by the investigator.

Topiramate Titration in Subjects 2 to <10 Years of Age

Dosing in subjects 2 to <10 years of age is based on weight. During the titration period, the initial dosage of topiramate should be 25 mg/day, administered nightly for the first week. Based upon tolerability, the dosage can be increased to 50 mg/day (25 mg BID) in the second week (see Tables 1 to 3 in the titration schedules in [Attachment 2](#)). Dosage can be increased by 25 to 50 mg/day each subsequent week as tolerated. Titration to the maximum recommended dosage should be attempted over 6 to 8 weeks. Based upon tolerability and seizure control, the rate of titration may be adjusted to achieve optimal clinical response. The total daily dosage should not exceed the maximum maintenance dosage for each range of body weight ([Table 1](#)). Subjects with a body weight >38 kg will be assigned to the titration schedule for subjects 10 to 15 years of age, as described below.

Table 1: Topiramate Monotherapy Target Total Daily Maintenance Dosing for Subjects 2 to <10 Years of Age

Weight (kg)	Total Daily Dosage (mg/day) ^a	
	Minimum Maintenance Dosage	Maximum Maintenance Dosage
Up to 11	150	250
12 – 22	200	300
23 – 31	200	350
32 – 38	250	350

^a Administered in 2 equally divided doses.

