meals. Study staff will instruct subjects and/or parents/caregivers on how to store medication for at-home use as indicated for this study. If a subject vomits within 30 minutes of receiving a dose, the dose will be repeated. If a subject vomits a second time or more than 1 hour later, the dose will not be repeated. All cases of vomited doses and action taken must be recorded in the subject's take-home record. Subjects will be instructed to take any missed doses of study drug as soon as possible. However, if the subject is within 6 hours of taking the next scheduled dose, he or she should wait until then to take the usual dose of study drug and skip the missed dose. Subjects should not take a double dose in case of a missed dose.

Subjects should be titrated and maintained according to clinical response, eg, titration may be slowed on the basis of tolerability and may be accelerated for the purposes of seizure control. Maintenance dosages should be based on optimal clinical response and may be adjusted at any time during the open-label treatment phase. Subjects are recommended not to exceed maximum recommended maintenance dosages; however, subjects will not be discontinued from the study if higher doses are required for optimal clinical effect as judged by the investigator. Data collected while on dosages that exceed maximal recommendations may be analyzed separately, as appropriate.

Once a subject completes the study or discontinues early from the study, at the discretion of the investigator, he or she will either continue on commercially available topiramate or levetiracetam or be tapered off of topiramate or levetiracetam over a period of up to 2 weeks.

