- a) Much less active on weekends than six months ago
- b) Somewhat less active on weekends than six months ago
- c) No real change in activity on weekends from six months ago
- d) Somewhat more active on weekends than six months ago
- e) Much more active on weekends than six months ago

You are finished now - Thank you for completing this form!

Attachment 2: Titration Schedules for Topiramate and Levetiracetam**Topiramate Monotherapy Titration Schedule for Subjects 2 to <10 Years of Age****Table 1:** Topiramate Monotherapy Titration Schedule for Subjects 2 to <10 Years of Age – Body Weight up to 11 kg (Maximum Recommended Maintenance Dosage 250 mg/day)

	Total Daily Dosage (mg)	Morning Dose (mg)	Evening Dose (mg)
Week 1	25	0	25
Week 2	50	25	25
Week 3	75	25	50
Week 4	100	50	50
Week 5	125	50	75
Week 6	150	75	75
Week 7	200	100	100
Week 8	250	100	150

Table 2: Topiramate Monotherapy Titration Schedule for Subjects 2 to <10 Years of Age – Body Weight 12 to 22 kg (Maximum Recommended Maintenance Dosage 300 mg/day)

	Total Daily Dosage (mg)	Morning Dose (mg)	Evening Dose (mg)
Week 1	25	0	25
Week 2	50	25	25
Week 3	75	25	50
Week 4	100	50	50
Week 5	150	75	75
Week 6	200	100	100
Week 7	250	125	125
Week 8	300	150	150

Table 3: Topiramate Monotherapy Titration Schedule for Subjects 2 to <10 Years of Age – Body Weight 23 to 38 kg (Maximum Recommended Maintenance Dosage 350 mg/day)

	Total Daily Dosage (mg)	Morning Dose (mg)	Evening Dose (mg)
Week 1	25	0	25
Week 2	50	25	25
Week 3	75	25	50
Week 4	100	50	50
Week 5	200	100	100
Week 6	250	125	125
Week 7	300	150	150
Week 8	350	175	175

Topiramate Monotherapy Titration Schedule for Subjects 10 to 15 Years of Age**Table 4:** Topiramate Monotherapy Titration Schedule for Subjects 10 to 15 Years of Age

	Morning Dose (mg)	Evening Dose (mg)
Week 1	25	25
Week 2	50	50
Week 3	75	75
Week 4	100	100
Week 5	150	150
Week 6	200	200

Levetiracetam Weight-Based Titration Dosing Guide (Oral Solution, 100 mg/mL) for Subjects With a Body Weight ≤20 kg**Table 5:** Levetiracetam Weight-Based Titration Dosing Guide (Oral Solution; 100 mg/mL) for Subjects With a Body Weight ≤20 kg – Weeks 1 to 2 (20 mg/kg/day)

Body Weight (kg)	Total Daily Dosage (mg)	Morning Dose (mg)	Evening Dose (mg)	Dosage Regimen
10	200	100	100	1.0 mL BID
11	220	110	110	1.1 mL BID
12	240	120	120	1.2 mL BID
13	260	130	130	1.3 mL BID
14	280	140	140	1.4 mL BID
15	300	150	150	1.5 mL BID
16	320	160	160	1.6 mL BID
17	340	170	170	1.7 mL BID
18	360	180	180	1.8 mL BID

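### Section 6 gives weekly topiramate steps of 25 to 50 mg/day for children under 10, but the default schedule for 23 to 38 kg contains one step of 100 mg/day; the schedule for up to 11 kg also splits its 250 mg/day maximum unequally

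*Protocol*

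**What the plan says.** The Protocol gives the titration instruction for topiramate subjects aged 2 to under 10 years in two places.

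- **Section 6, text.** "Dosing in subjects 2 to <10 years of age is based on weight". The starting dosage is 25 mg/day in Week 1, with 50 mg/day possible in Week 2. For the weeks that follow: "Dosage can be increased by 25 to 50 mg/day each subsequent week as tolerated". The same paragraph refers to Attachment 2, Tables 1 to 3, and aims for the maximum recommended dosage over 6 to 8 weeks.
- **Section 6, flexibility.** The paragraph adds: "Based upon tolerability and seizure control, the rate of titration may be adjusted to achieve optimal clinical response". Later in the section: "titration may be slowed on the basis of tolerability and may be accelerated for the purposes of seizure control".
- **Section 6, Table 1.** This lists minimum and maximum maintenance dosages by weight band. Its footnote reads: "Administered in 2 equally divided doses".
- **Attachment 2, Table 3.** The title specifies "Body Weight 23 to 38 kg (Maximum Recommended Maintenance Dosage 350 mg/day". The columns are total daily, morning and evening dose. Two consecutive rows read "Week 4 100 50 50" and "Week 5 200 100 100".
- **Attachment 2, Table 1 (up to 11 kg).** Week 8 gives 250 mg/day, the maximum for that band, as 100 mg in the morning and 150 mg in the evening.

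**The concern.** The text and the schedule it points to should give the same default. In the 23 to 38 kg band they do not. For a child at 100 mg/day in Week 4, the text leads to 125 to 150 mg/day in Week 5, while Table 3 gives 200 mg/day. Two sites that each follow the Protocol in good faith, one from the text and one from the table, would differ by 50 to 75 mg/day in that week.

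The second conflict is smaller and concerns a different weight band. At 250 mg/day in the lightest children, the footnote implies 125 mg twice daily, while Attachment 2 prints 100 mg and 150 mg.

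What is at stake is clear dosing instructions in a paediatric safety study of topiramate. No endpoint or analysis is directly affected.

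**Working it through.** **Inputs.** The stated range is 25 to 50 mg/day per week after Week 2 (Section 6). Total daily dosages by week are from Attachment 2, Tables 1 to 3.

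**Step 1: check that Table 3 is read correctly.** Morning plus evening dose, Weeks 1 to 8: 0+25, 25+25, 25+50, 50+50, 100+100, 125+125, 150+150, 175+175. The sums are 25, 50, 75, 100, 200, 250, 300, 350 mg/day and match the printed totals in all eight weeks. The step is not an artefact of a broken table.

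**Step 2: weekly steps.** Step = total in this week − total in the week before.

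| Attachment 2 schedule | Totals, Weeks 1 to 8 (mg/day) | Steps (mg/day) |
|---|---|---|
| Table 1, up to 11 kg | 25, 50, 75, 100, 125, 150, 200, 250 | 25, 25, 25, 25, 25, 50, 50 |
| Table 2, 12 to 22 kg | 25, 50, 75, 100, 150, 200, 250, 300 | 25, 25, 25, 50, 50, 50, 50 |
| Table 3, 23 to 38 kg | 25, 50, 75, 100, 200, 250, 300, 350 | 25, 25, 25, **100**, 50, 50, 50 |

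Of 3 × 7 = 21 steps, 20 lie within 25 to 50 mg/day. The exception is 200 − 100 = 100 mg/day, which is 100/50 = 2 times the top of the range.

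**Step 3: Week 5 by each instruction.** Text: 100 + 25 = 125 to 100 + 50 = 150 mg/day. Table: 200 mg/day. Gap: 200 − 150 = 50 to 200 − 125 = 75 mg/day.

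**Step 4: does Table 3 run ahead of the text overall?** Take the top of the text's range throughout, 50 mg/day in Week 2 and then +50 each week. This is arithmetic only, not a proposed schedule.

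| Week | 2 | 3 | 4 | 5 | 6 | 7 | 8 |
|---|---|---|---|---|---|---|---|
| +50 each week | 50 | 100 | 150 | 200 | 250 | 300 | 350 |
| Table 3 | 50 | 75 | 100 | 200 | 250 | 300 | 350 |

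Table 3 is lower in Weeks 3 and 4 and identical from Week 5. Its average rise over Weeks 2 to 8 is (350 − 50)/6 = 50 mg/day per week, which is within the range. The same comparison shows that the 8-week target does not force the large step, because steps of 50 also reach 350 mg/day in Week 8.

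**Step 5: the split.** In the up-to-11 kg band the maintenance range in Section 6 Table 1 is 150 to 250 mg/day. Attachment 2 Table 1 gives 150 as 75 + 75, 200 as 100 + 100 and 250 as 100 + 150. Only the maximum is unequal. An equal split of 250 mg/day is possible, since Attachment 2 Table 2 (Week 7) and Table 3 (Week 6) both print it as 125 + 125.

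**The case against.** The strongest reply is that Section 6 gives a guide range and not a cap. It says what can be done, as tolerated, and lets the investigator change the rate. Sections 3.1 and 9.1.3 say much the same. An investigator who follows Table 3 in Week 5 can point to those clauses. This stands as far as it goes, and it rules out describing the text as a strict limit. It does not remove the conflict. The flexibility clauses concern departures for an individual child, whereas Table 3 is the default for everyone in the band, and no section mentions or explains a 100 mg/day step.

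Four stronger readings are tempting, and the documents do not support them.

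- A reader might infer that these children are titrated at twice the intended rate. Step 4 shows otherwise: one weekly step is doubled, and the daily dose never passes what the text's own range could reach.
- A reader might take the doubling of the dose, from 100 to 200, as the anomaly. Text and tables agree on a doubling from 25 to 50 mg/day in Week 2. What conflicts is the absolute size of the later step.
- A reader might infer that following one page would be logged as a protocol deviation. SAP Section 5.5 has a major-deviation category that covers dose deviations, but nothing says that following either titration instruction falls in it.
- A reader might apply the point to every child under 10 in the band. It applies only to those assigned to topiramate (half, under 1:1 randomisation), and only if they escalate as scheduled to Week 5.

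Attachment 2 Table 4 also has 100 mg/day steps (200 to 300 to 400). It serves ages 10 to 15 and younger children above 38 kg, and Section 6 ties the 25 to 50 mg/day sentence to Tables 1 to 3, so it is not counted here.

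**Conclusion.** There are two internal inconsistencies, both confirmed by arithmetic on the printed tables. The first is one step of 100 mg/day, Week 4 to Week 5 in Attachment 2 Table 3, against a stated 25 to 50 mg/day; the two instructions differ by 50 to 75 mg/day in Week 5. The second is one unequal split, 100 + 150 mg at the 250 mg/day maximum in Attachment 2 Table 1, against a footnote requiring equal doses.

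The conclusion assumes that the Section 6 sentence applies to all three weight-band tables cited in its paragraph, and that those tables are the default schedules. It does not depend on which instruction is clinically right, and that is not judged here.

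The point is worth correcting because it concerns default paediatric dosing and the correction is simple. It should not be presented as excess dosing or as a threat to the growth, bone or kidney-stone analyses: the study is flexible-dose, and no planned estimate is shown to change.

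**What to change.** Reconcile the Section 6 titration text with Attachment 2 Table 3, and the footnote to Section 6 Table 1 with Attachment 2 Table 1, so that text and schedule give one default step and one default split. If the Week 5 step or the unequal split is intended, Section 6 should say so. Which step and which split apply is for the sponsor's clinical team.

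The cost is a protocol clarification or a letter to sites, with no change to sample size, data collection or analysis. SAP Section 1 records the August 2019 decision to stop enrolling new subjects, so by the date of the current SAP a letter would do little for dosing. The discrepancy could then be noted in the study report where the titration schedules are described.

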7. TREATMENT COMPLIANCE

The investigator or designated study personnel will maintain a log of all drug dispensed and returned. Drug supplies for each subject will be inventoried and accounted for throughout the study (at each visit). Subjects will receive instructions on compliance with study treatment at the screening visit (eg, subject take-home record). During the course of the study, the investigator or designated study research staff will be responsible for providing additional instruction to reeducate any subject who is not compliant with taking the study drug.

8. PRESTUDY AND CONCOMITANT THERAPY

Prestudy AEDs and other medications taken within 2 years prior to the study must be recorded at screening.

Concomitant therapies must be recorded throughout the study beginning with the start of the first dose of study drug. Concomitant therapies should also be recorded beyond 30 days after the last dose of study drug, but only in conjunction with new or worsening adverse events or serious adverse events that meet the criteria outlined in Section [12.3.2](#), Serious Adverse Events.

All therapies (prescription or over-the-counter medications, including vaccines, vitamins, herbal supplements; non-pharmacologic therapies such as electrical stimulation, acupuncture, special diets, exercise regimens) different from the study drug must be recorded in the CRF. Modification of an effective preexisting therapy should not be made for the explicit purpose of entering a subject into the study.

For subjects receiving an AED at baseline, this AED should be tapered down and discontinued during the titration period. Concomitant AEDs at baseline used for any purpose will be withdrawn in one-third decrements during the 6- to 8-week titration period.

Only AED monotherapy will be used for both treatment groups. In the event of insufficient seizure control or intolerability, it should be explored first if a dosage adjustment of the study drug might be useful before adding another AED. However, subjects will not be discontinued from the study if 1 or more concomitant AEDs are added after initiating treatment with study drug. Data will be collected prior to the use of the concomitant AED(s) for the primary analysis. Data subsequently collected while on the concomitant AED(s) will be analyzed in a secondary analysis for each safety outcome of interest.

Other prohibited concomitant medications include:

- Ocular medications, except lubricating eye drops or topical antibiotics
- Furosemide, hydrochlorothiazide, vigabatrin, vitamin B₆ therapy for epilepsy, monoamine oxidase (A or B) inhibitors, or felbamate
- Any other medication that is a potent carbonic anhydrase inhibitor (eg, acetazolamide, furosemide, zonisamide)
- Citrate treatment
- Medications that may affect bone metabolism taken for more than a 10-day treatment course, including intravenous or oral steroids, growth hormone, NSAIDs, antacids, calcium, vitamin D, or multivitamins

Subjects will be allowed to take calcium, vitamin D, and multivitamins as concomitant therapy provided the dosages fall within the range of recommended daily allowances for the age of the subject. These agents will only be allowed as prophylaxis against a deficiency, and not as a treatment for a previously diagnosed deficiency.

The sponsor must be notified in advance (or as soon as possible thereafter) of any instances in which prohibited therapies are administered.

9. STUDY EVALUATIONS

9.1. Study Procedures

9.1.1. Overview

The Time and Events Schedule that follows the synopsis summarizes the frequency and timing of safety, PK, and other measurements applicable to this study.

The study includes 3 phases: a screening phase of up to 35 days, an open-label treatment phase of 1 year's duration (including titration and maintenance), and a posttreatment phase of 30 days, during which subjects will either continue on commercially available topiramate or levetiracetam or will be tapered off of topiramate or levetiracetam over a period of up to 2 weeks. There may be an optional post-study follow-up phase to obtain DEXA measurements in a subgroup of subjects who experience a clinically important reduction (change in Z-score of -0.5 or greater) in BMD, based on local DEXA scan results, after 1 year of treatment with topiramate, to determine whether a decrease in BMD after or during 1 year of treatment with topiramate is reversible. These subjects will have a repeat DEXA scan 6 months after discontinuation of study drug.

The total blood volume to be collected from each subject will be approximately 44.7 mL (45.8 mL for adolescent girls who require serum pregnancy test at screening; [Table 2](#)). Blood samples for testing specific analytes are listed in order of priority, in the event of difficulties in obtaining the desired volume of blood for any reason at a specific visit. Repeat or unscheduled samples may be taken for safety reasons or for technical issues with the samples.

Table 2: Volume of Blood to be Collected From Each Subject (mL)

Visits	Screening ^a	Month 1	Month 3	Month 6	Month 9	Month 12	Total Volume of Blood ^b
Blood chemistry profile, including electrolytes	1.1	1.1	1.1	1.1	1.1	1.1	6.6
CBC (EDTA whole blood)	1.2	1.2	1.2	1.2	1.2	1.2	7.2
25-hydroxy-vitamin D ^c	1.1			1.1		1.1	3.3
IGF-1 ^c	1.1			1.1		1.1	3.3
Parathyroid hormone (intact) ^c	1.1			1.1		1.1	3.3
1,25-dihydroxy-vitamin D ^c	3.0			3.0		3.0	9.0
Ammonia, venous ^c	1.2	1.2	1.2	1.2	1.2	1.2	7.2

Table 2: Volume of Blood to be Collected From Each Subject (mL)

Visits	Screening ^a	Month 1	Month 3	Month 6	Month 9	Month 12	Total Volume of Blood ^b
Pharmacokinetic samples (plasma; AED levels)		1.2	1.2	1.2		1.2	4.8
Serum pregnancy test	1.1						1.1
Total	10.9 mL	4.7 mL	4.7 mL	11.0 mL	3.5 mL	11.0 mL	45.8 mL

a The optional use, during the screening period, of local laboratory evaluations for 25-hydroxy-vitamin D, 1,25-dihydroxy-vitamin D, Parathyroid hormone (intact) and IGF-1 might lead to an increase in blood volume for the subject concerned. The total volume is dependent on the local laboratory requirements and on the number and type of individual assays.

b Calculated as number of samples multiplied by amount of blood per sample.

c All laboratory tests will be evaluated centrally except for venous ammonia, which will be evaluated locally (except in select countries where local testing is not possible, in which case the central laboratory will also evaluate venous ammonia). The laboratory tests for 25-hydroxy-vitamin D, 1,25-dihydroxy-vitamin D, Parathyroid hormone (intact) and IGF-1 at screening will be evaluated centrally but additional evaluation at local laboratory is allowed to reduce the duration of the screening phase. At the discretion of the investigator, one, or more of these laboratory parameters may be evaluated at the local laboratory. The volume of blood is based on reference laboratory minimal volumes.

AED=antiepileptic drug; CBC=complete blood count; EDTA= ethylene diamine tetra-acetic acid; IGF-1=insulin-like growth factor 1.

9.1.2. Screening Phase

The screening phase will last up to 35 days, during which subjects will be assessed for study qualifications and other measures as listed in the Time and Events Schedule following the synopsis.

9.1.3. Open-Label Treatment Phase

The open-label treatment phase includes randomization and distribution of study drug and titration instructions (Visit 2; Day 1), a 6- to 8-week titration period, and a maintenance period, during which subjects will remain in the study until they either complete 1 year of open-label treatment or withdraw from the study.

Subject take-home records and seizure diaries will be given to parents/guardians at Visit 1 and at each subsequent visit. Each subject's parent will record in the seizure diary the date, description, and number of seizures. The investigator or designated study personnel will review the data to be recorded in the subject take-home record with the subject's parents/legally acceptable representatives at the beginning of the study. At each visit, the investigator will review the seizure data, and then transcribe the data onto the appropriate page of the CRF.

Titration intervals and dosages may be adjusted for individual subjects to achieve their optimal dosage. Subjects receiving 1 concomitant AED at baseline for any purpose will have their AED tapered down and discontinued in one-third decrements during the 6- to 8-week titration period.

At the end of the titration period, the dosage of study drug should be maintained but may be adjusted at the investigator's discretion for optimal clinical effect.

Subjects will return for a clinic visit at Months 2 and 3, with subsequent visits to occur every 3 months.

9.1.4. Posttreatment Phase (Follow-Up)

Subjects who complete the study or discontinue early from the study may at the discretion of the investigator either continue on commercially available topiramate or levetiracetam or be tapered off of topiramate or levetiracetam over a period of up to 2 weeks during the posttreatment phase. A final visit will be performed at the end of the 1-year open-label treatment period or upon early withdrawal, including review of seizure frequencies from the subject seizure diary and review of safety and adverse events.

Telephone contact will be made to assess adverse events and concomitant medications 30 days after the last dose of study drug, unless the subject has died, is lost to follow-up, or has withdrawn consent/assent. If the information on adverse events and concomitant medications is obtained via telephone contact, written documentation of the communication must be available for review in the source documents. If the subject has died, the date and cause of death must be collected and documented on the CRF.

